7.3.12 Serum Ferritin

All the determinations relative to serum ferritin will be carried out on the same sample collection as haematology/biochemistry at screening, and at each monthly visits for evaluation at the local laboratory for patient clinical monitoring.

Additional serum ferritin determinations will be performed in blood collected in separate vials at V3, V6, V9, V12, V15 and will be evaluated in the centralised laboratory/ies as specified in the SPM. Central determination of ferritin will be performed also in case of withdrawal during the early termination visit. Central determinations will be used for formal analyses.

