11.2 Study population

Intent to treat population

For the intent to treat (ITT) analysis all patients that have been randomized and start therapy will be included.

Per protocol population

Patients in the per protocol (PP) population for the primary efficacy analysis (PP1) are those that have received the study drugs and for whom the composite endpoint is available at baseline and after 1 year treatment, without major protocol violations.

For the secondary efficacy evaluation assessed as non-inferiority of DFP to DFX in terms of serum ferritin levels the PP population (PP2) includes only patients for whom the measure of serum ferritin is available at baseline and after 1 year treatment.

For the secondary efficacy evaluation assessed as non-inferiority of DPF to DFX in terms of successfully chelated patients according to cardiac MRI T2* the PP population (PP3) includes only patients for whom the measure cardiac MRI T2* is available at baseline and after 1 year treatment.

Safety population

The population for the safety and tolerability analysis will include all patients having received at least one dose of study medication.

PK and PKPD population

The population for the pharmacokinetic and subsequent exploratory analyses (e.g. correlation between systemic exposure and ferritin levels) will include patients who have received the investigational drugs throughout the duration of the study (i.e., 1 year) and have had a blood sample collected for the assessment of drug concentrations in plasma.

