Serum ferritin will be tested in terms of quantitative variable as part of the composite endpoint measurable in the entire experimental population. The purpose of this analysis is to clarify the interpretation of the primary composite endpoint and hence no adjustment for multiplicity will be considered. The population for this analysis is the PP2. ITT analysis will be used to corroborate the findings.

Non inferiority of DFP to DFX will be tested considering a non inferiority margin of 400 ng/mL.

Non-inferiority will be assessed based on the two sided 95% confidence interval $[\delta_L, \delta_U]$ of the difference $\delta = m_1 - m_2$, being m_1 and m_2 the mean difference between baseline and end of treatment assessments of DFP and DFX, respectively, and n_1 and n_2 the numbers of patients randomised to DFP and DFX arms. Non-inferiority will be claimed if δ_L is greater than -400 ng/ml.

The two sided 95% confidence interval for δ will be estimated as follows:

$$(m_1 - m_2) \pm Z_{1-\alpha/2} \sigma \sqrt{\frac{1}{n_1} + \frac{1}{n_2}}$$

where Z_γ is the γ^{th} percentile of the standardised normal distribution and σ^2 is the pooled variance.

Serum ferritin trends over the 1 year period of treatment will be also investigated. A repeated measures analysis of variance model with treatment-group as main effect will be fitted. The H_0 of equal between group regression slopes will be tested by evaluating whether the interaction between the categorical factor (treatment group) and the repeated measure (monthly measures of serum ferritins) equals zero, i.e. no interaction. The rejection of the null hypothesis on the interaction term (treatment group*monthly ferritin measure) will be supportive of different trends between DFP and DFX arms. The ITT population will be used for this analysis. Handling of missing data for this analysis is described in Section 11.4.

Descriptive statistics for trends in subgroups of patients according to age classes will be also provided.

Efficacy measured through cardiac T2* MRI

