11.12 Sample Size and power considerations

Primary efficacy objective

Assuming type I and type II errors of 0.025 and 0.20, respectively, and a one-sided test, and under the assumptions that the expected proportion of subjects declared treatment successes in the DFX arm is 65%, and the expected proportion of subjects declared treatment successes in the DFP arm is 67.5% a sample size of 310 subjects, randomized in a 1:1 ratio to DFP or DPX will yield 80% power to demonstrate non-inferiority of DFP versus DFX. Taking into account a possible dropout rate of about 20% a total enrolment of 388 patients aged from 1 month to less than 18 years are expected to be included in the trial.

Secondary efficacy objective

Sample size requirements for the secondary efficacy objectives (non-inferiority in terms of ferritin levels and cardiac MRI T2*) are provided in the following.

Based on published literature, testing for non-inferiority is appropriate also when comparing DFP to DFX efficacy in terms of serum ferritin levels. In this case, considering a hypothesis testing on the continuous measure, a non inferiority margin of 400 ng/ml is considered a reliable estimate of the true allowed maximum difference between the IMPs in order to assume DFP to be non-inferior to DFX in controlling iron overload in patients affected by hereditary haemoglobinopathies. The standard deviation of the differences is available by pooling findings from paediatric studies conducted in Europe and outside (El Alfay M et al., 2010), and a reliable and conservative estimate can be 1000 ng/mL.

On these assumptions, 310 evaluable patients are sufficient to provide at least 90% power to demonstrate non inferiority of DFP to DFX, assuming a type I error of 0.025 and a one-sided test.

When considering efficacy in terms of cardiac MRI T2*, less reliable estimates of treatment efficacy are available, especially in the paediatric population. However, there are no reasons for not assuming at least a non inferiority of DFP to DFX, considering also the known beneficial effects of DFP at the cardiac level. Based on the limited published figures of cardiac MRI T2* in the paediatric population and taking into account adult data, some plausible scenarios of sample sizes and related powers are provided in the following **Table 7**, assuming a type I error of 0.025 and a one-sided test. Detailed power curves will be provided in the statistical plan.

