11.13 Handling of missing data

A negligible amount of missing data is expected in this study because the patient population under study (patients affected by haemoglobinopathies requiring chronic transfusion and chelation therapy), and their parents, are accustomed to routine close monitoring in clinical visits, are used to frequent lab tests and comply with uncomfortable examinations (MRI), and are generally willing to participate in trials that may lead to increasing the availability of treatments. Moreover, the estimated treatment effect is not expected to be importantly biased in favour of the experimental treatment due both to the choice of the comparator and of the primary endpoint.

DFX is an oral chelator as DFP, and its compliance is expected to be comparable to that of DFP, or even better taking into account the once a day administration.

The completeness of the data that will allow the estimate of the primary endpoint (percentage of successfully chelated patients) is expected to be high due to the type of patients and condition.

Finally, patients who prematurely discontinue the trial for any reason will be considered treatment failures.

Assuming the worst scenario for incomplete data in order to provide conservative estimates for the trial results, the imputation of missing data will only apply to missing data because of a missing visit. This will affect the trend analysis for the secondary evaluation on serum ferritin levels. In this case, Linear Mixed Models (LMM) will be used as imputation method for missing data.

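### The ITT check on the secondary ferritin non-inferiority test has no rule for patients without a month-12 value, and on the natural reading it repeats PP2

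*Combined protocol and SAP*

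**What the plan says.** - **The test.** Section 11.6 compares the arms on the mean difference between baseline and end-of-treatment ferritin: "Non-inferiority will be claimed if δ_L is greater than -400 ng/ml". On the analysis sets: "The population for this analysis is the PP2. ITT analysis will be used to corroborate the findings".
- **The sets.** Under Section 11.2, ITT is everyone randomised who starts therapy. PP2 "includes only patients for whom the measure of serum ferritin is available at baseline and after 1 year treatment". The PP1 definition also excludes major protocol violations; the PP2 definition does not mention them.
- **End of treatment.** Section 7.1 identifies this with month 12 (V15), and Section 7.2.4 makes V15 the last on-treatment evaluation.
- **Missing data.** Section 11.13 states that "the imputation of missing data will only apply to missing data because of a missing visit", and then ties this to the ferritin trend analysis, using linear mixed models. Sections 9 and 11.13 class premature withdrawals as treatment failures. Section 11.6 scores a non-estimable composite as a failure in the primary ITT analysis.
- **Withdrawal.** Section 9 lists a quarterly ferritin rise of at least 1500 ng/mL among the reasons for discontinuation. Section 7.3.12 adds: "Central determination of ferritin will be performed also in case of withdrawal during the early termination visit". It also says that central results feed the formal analyses, without saying whether the withdrawal result enters this test.
- **Cross-reference.** For missing data in the trend analysis, Section 11.6 points to Section 11.4, which covers demographics. The text is in Section 11.13.

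**The concern.** An ITT analysis supports a per-protocol non-inferiority result only if it brings back patients whom the per-protocol set leaves out. Here the quantity tested is a mean change that needs two ferritin values, and PP2 is defined by having those same two values. If ITT patients without a month-12 value simply fall out, the second analysis agrees with the first by construction.

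The patients who fall out are not a random subset. One reason for leaving the study is a steep ferritin rise, which is the outcome being measured. If the arms differ in how many patients leave for that reason, both analyses share the same bias, and their agreement would look like reassurance. Section 4.4.1 gives this test the role of supporting treatment efficacy, and Section 11.12 gives it its own margin and power statement, so the corroboration should carry information.

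**Working it through.** **1. The plan's own figure.** Inputs from Section 11.12: margin 400 ("a non inferiority margin of 400 ng/ml is considered a reliable estimate of the true allowed maximum difference between the IMPs"), SD 1000 ("a reliable and conservative estimate can be 1000 ng/mL"), one-sided 0.025 ("demonstrate non inferiority of DFP to DFX, assuming a type I error of 0.025 and a one-sided test"), and 310 evaluable patients, so 155 per arm. No true difference is stated for ferritin; I assume 0.

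- SE = 1000 × √(2/155) = 113.6 ng/mL.
- Power = Φ(400/113.6 − 1.96) = Φ(1.56) = 94.1%, which agrees with the stated figure of at least 90%.
- Confidence interval half-width = 1.96 × 113.6 ≈ 223 ng/mL.

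Power is not the problem.

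**2. Can any stated rule bring in an ITT patient without a V15 ferritin?**

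| Rule | Where | Supplies a value for the mean change? |
|---|---|---|
| Non-estimable composite is a failure | 11.6, primary | No: composite only, binary |
| Premature withdrawal is a failure | 9, 11.13 | No: binary |
| Mixed-model imputation | 11.13 | No: missed visits only, tied to the trend analysis |
| Central ferritin at withdrawal | 7.2.5, 7.3.12, Table 5 footnote | Collected; whether it counts as end of treatment is not stated |

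With end of treatment read as V15 and both values required, the contributing patients are those with baseline and V15 ferritin. That is PP2 as worded.

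**3. How many patients.** 310/0.80 = 387.5, rounded up to 388. The allowance is 388 − 310 = 78 patients, or 39 per arm if evenly split.

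**4. Illustration of the shift.** None of these inputs is a document figure except the 1500 threshold, which I borrow as a net change:

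- withdrawn patients carry a net rise of 1500 ng/mL;
- completers in both arms have the same mean reduction R, with R = 0, 300 or 600;
- the DFP arm has e more such withdrawals, as a proportion, than the DFX arm.

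I take change as baseline minus end, so that a reduction is positive, which fits the sign of the decision rule. Retaining the withdrawn patients moves the DFP minus DFX difference by −(1500 + R) × e. With e = 0.05 (0.05 × 194 = 9.7 patients):

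- R = 0: −1500 × 0.05 = −75, and 75/400 = 19% of the margin.
- R = 300: −1800 × 0.05 = −90, and 90/400 = 22.5%.
- R = 600: −2100 × 0.05 = −105, and 105/400 = 26%.

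With the excess on DFX the signs reverse.

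**5. Position against the margin.** Assume further that 5% of the DFX arm is so withdrawn and that all 194 per arm contribute. With w the proportion so withdrawn in an arm, each arm's variance is V = 1000² + (1500 + R)² × w(1 − w). The expected lower limit is the shift minus 1.96 × √[(V₁ + V₂)/194].

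| R | Lower limit, 5-point DFP excess | Lower limit, 10-point DFP excess |
|---|---|---|
| 0 | −289 | −368 |
| 300 | −310 | −405 |
| 600 | −332 | −444 |

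A completers-only analysis would show a difference of 0 and a lower limit near −223 throughout. A 5-point excess leaves the conclusion standing. A 10-point excess takes the limit past −400 in two of the three cases.

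**The case against.** The strongest reply is that the plan is silent, and silence does not prescribe a complete-case analysis. A reader might infer that the ITT analysis must drop these patients and must agree with PP2. The documents do not go that far. Section 11.2 puts every treated randomised patient in ITT, and Section 11.6 describes n₁ and n₂ as numbers randomised. That phrase settles little, since it serves PP2 and ITT alike and also appears in the primary analysis, which is run on PP1. Still, complete-case analysis is the natural reading, not an express instruction.

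A reader might also infer that the withdrawal ferritin is excluded from this comparison. Section 7.3.12 provides for its collection and says that central values serve formal analyses. Its use here is unspecified, not ruled out.

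PP2 is labelled a per-protocol set, so the PP1 violation clause might be meant to carry over. In that case ITT would add completers with violations. It would still not add withdrawn patients, so the main gap remains. Likewise, missed-visit imputation might be stretched to a missed V15 in a patient still on study, but not to a withdrawal.

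The consequence is limited, and this part of the reply stands. The test is secondary. Withdrawals count as failures in the primary ITT analysis, and neither the primary claim nor the step to superiority depends on this test. The ITT trend analysis can use ferritin measured before withdrawal, but it tests for different slopes and has no margin, so it cannot stand in for the missing check.

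**Conclusion.** The plan gives no rule by which a patient without a month-12 ferritin contributes to the ITT version of the -400 ng/mL test. Read naturally, that analysis repeats PP2 and leaves out patients withdrawn for steeply rising ferritin. This is more than a missing detail, because following the stated formula and imputation limit produces a check that cannot disagree with what it checks.

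Three readings of the size should be resisted:

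- The 78 patients are a planning allowance for possible dropout, set for the primary objective. They are not a forecast of missing ferritin: Section 11.13 expects negligible missing data, and PP1 also requires MRI where applicable, so more than 310 patients may be evaluable for ferritin.
- The 75 to 105 ng/mL is not a floor. The 1500 ng/mL threshold is a quarterly rise, so net change from baseline can be smaller. If completers rose by 300 on average, a 5-point excess would shift the difference by 0.05 × 1200 = 60 ng/mL.
- Nothing in the documents says which arm would lose more such patients, so the bias has no known direction.

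The conclusion rests on reading end of treatment as V15 and on PP2 as worded. The primary composite ITT analysis is unaffected. I would ask for the change, but it is not a threat to the primary result.

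**What to change.** - Define the ITT ferritin analysis as a likelihood-based mixed model of central ferritin at V3, V6, V9, V12, V15 and the withdrawal visit, the last entered at its actual time. Estimate the month-12 treatment difference with its two-sided 95% interval and compare it with the same -400 ng/mL margin.
- Add a sensitivity analysis for patients withdrawn for unsatisfactory effect: tipping-point, reference-based, or using the withdrawal-visit value.
- State whether PP2 carries the major-violation exclusion, and whether the withdrawal ferritin may count as an end-of-treatment value.
- Correct the missing-data pointer in Section 11.6 from Section 11.4 to Section 11.13.

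The cost is SAP wording and a little more analysis; the plan already schedules these ferritin measurements. The main model relies on data being missing at random, which withdrawal for unsatisfactory effect may strain. The sensitivity analysis is there to address that.

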The target patient population consists of 388 outpatients affected by hereditary haemoglobinopathies requiring chronic transfusion and chelation, randomized 1:1 in two groups of 194 patients each to ensure 310 evaluable patients. Chelation naïve and not naïve patients aged from 1 month to less than 18 years will be recruited. A staggered approach will be applied to patients aged less than 6 years (10% of the total sample), which will be recruited after results from the PK Study (Study DEEP-1, EudraCT n. 2012-000658-67) will be available.

Experimental arm: patients administered with DFP at 75-100 mg/kg/day for seven days per week. In patients aged less than 6 years the dose will be defined according to the results of the PK Study (Study DEEP-1, EudraCT n. 2012-000658-67). DFP daily dose will not exceed 100 mg/kg.

Control arm: patients administered with DFX at 20-40 mg/kg/day as recommended by the currently approved European SmPC (last update 10/08/2011). DFX daily dose will not exceed 40 mg/kg.

Details on the starting dose and subsequent dose adjustments are reported in **Section 6**.

The **treatment duration** for both groups is 12 months.

4.1Non-inferiority margin

This study is designed to demonstrate the **non-inferiority** of a new liquid DFP (80 mg/mL) formulation in comparison with DFX in terms of percentage of successfully chelated patients as described in **Section 4.3**.

DFP will be declared non inferior to DFX if the lower limit of the 95% confidence interval for the difference in the proportion of successful chelation in the two groups is above -12.5%. The choice of this margin is based on clinical considerations starting from the available evidences for the effects of DFX at both ferritin and cardiac levels. For details please refer to **Section 11**.

4.2Choice of comparator

DFP will be compared to the oral chelating agent DFX. The rationale for comparing two oral chelators derives from the recent literature data reporting that oral chelating agents currently represent the most widespread adopted therapy in the paediatric age, due to good compliance, improved QoL and reduced burden of the disease (Ceci A et al, 2011).

4.3Primary endpoint

The primary endpoint will be the measure of treatment efficacy defined as the percentage of patients successfully chelated, as assessed by serum ferritin levels (in all patients) and cardiac MRI T2* (in patients above 10 years of age able to have an MRI scan without sedation).

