11.6 Efficacy evaluation

Primary efficacy

The primary efficacy evaluation will be based on a treatment success rate defined in Section 4.3 Primary endpoint. The primary analysis will be based on the PP1 population.

In addition, an ITT analysis will be performed to corroborate the findings. If no composite endpoint is estimable at 1 year treatment (unavailability of serum ferritin and/or MRI determination either at baseline or after 1 year treatment), the subject is considered a treatment failure in the ITT analysis. Non-inferiority will be assessed based on the two sided 95% confidence interval $[\delta_L, \delta_U]$ of the difference $\delta = p_1 - p_2$, being p_1 and p_2 the proportion of success in the n_1 and n_2 patients randomised to DFP and DFX arms, respectively. Non-inferiority will be claimed if δ_L is greater than -0.125. The two sided 95% confidence interval for δ will be estimated based on asymptotic normal approximation for the difference of two binomial probabilities as follows:

$$(p_1 - p_2) \pm Z_{1-\alpha/2} \sqrt{Var(p_1 - p_2)}$$

where Z_γ is the γ^{th} percentile of the standardised normal distribution and

$$Var(p_1 - p_2) = p_1(1 - p_1)/n_1 + p_2(1 - p_2)/n_2$$

If non-inferiority of DFP to DFX is established based on the PP1 population and the confidence interval for the null hypothesis of non-inferiority based on the ITT population is similar or the percentage of success for DFP is greater than that of DFX in magnitude, the hypothesis that DFP is superior to DFX in terms of the defined success criteria will be tested at the one-sided alpha level of 0.025. Superiority testing will be based on the ITT population. The rationale for superiority is justified by the known beneficial effects of DFP at the cardiac level.

Secondary efficacy

Efficacy measured through serum ferritin levels

Serum ferritin will be analysed as secondary measure of treatment efficacy. Serum ferritin is a well validated and clinically widespread surrogate measure of iron load, highly correlated with iron in the liver. It represents an easy to assess parameter in the paediatric population.

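### The ferritin non-inferiority interval takes n as the numbers randomised although the analysis is on PP2; the composite formula has a related mismatch with PP1

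*Combined protocol and SAP*

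**What the plan says.** Section 11.6 gives two confidence-interval formulas for non-inferiority.

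- **Serum ferritin (secondary).** The interval is (m_1 − m_2) ± Z·σ·√(1/n_1 + 1/n_2), with σ² the pooled variance and n_1, n_2 defined as "the numbers of patients randomised to DFP and DFX arms". On the population, the same section says: "The population for this analysis is the PP2. ITT analysis will be used to corroborate the findings". Section 11.2 states that PP2 "includes only patients for whom the measure of serum ferritin is available at baseline and after 1 year treatment".
- **Composite success (primary).** Section 11.6 states: "The primary analysis will be based on the PP1 population". The formula then defines p_1 and p_2 as "the proportion of success in the n_1 and n_2 patients randomised to DFP and DFX arms". Immediately before it stands the rule for a composite that cannot be determined: "the subject is considered a treatment failure in the ITT analysis".

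For ITT, section 11.2 specifies that "all patients that have been randomized and start therapy will be included". Section 4 sets the planned numbers: "randomized 1:1 in two groups of 194 patients each to ensure 310 evaluable patients". No section redefines n_1 and n_2 for PP1 or PP2.

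**The concern.** A standard error must use the number of patients who contributed to the estimate. In the ferritin formula the means and the pooled variance come from PP2, while the divisor is the larger number randomised. Every randomised patient who is missing from PP2 therefore shrinks the standard error without adding information. In a non-inferiority test a narrow interval makes the claim easier to reach, so the error runs in the experimental drug's favour.

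The composite formula has a different fault. Its proportions and its n refer to the same patients, but those patients are not the PP1 set on which the primary analysis is to be run. They are not exactly the ITT set either, because ITT also requires that therapy was started. The n in the text thus matches no defined analysis set, and whoever programs the analysis has to decide what was meant.

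**Working it through.** **Inputs.** Randomised 194 and evaluable 155 per arm (section 4: 388 and 310 in total). Dropout about 20%, success rates 65% (DFX) and 67.5% (DFP), one-sided alpha 0.025, and ferritin SD 1000 ng/mL (section 11.12). Margins 12.5 percentage points and 400 ng/mL (section 11.6).

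**Step 1: the plan's own figures, on evaluable patients.**

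- Composite: n per arm = (1.96 + 0.842)² × (0.65×0.35 + 0.675×0.325) / (0.125 + 0.025)² = 156, or 312 in total against 310 stated. Power at 155 per arm is 79.8%.
- Dropout: 310 / (1 − 0.20) = 388.
- Ferritin: SE = 1000 × √(2/155) = 113.6, and power = Φ(400/113.6 − 1.96) = 94.1%. The stated minimum of 90% is met; 132 per arm would suffice for it.

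The design figures therefore reproduce with n as the patients analysed.

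**Step 2: the ferritin interval with n as written.**

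- n = 155: half-width = 1.96 × 113.6 = 222.6 ng/mL.
- n = 194: SE = 1000 × √(2/194) = 101.5, half-width = 199.0 ng/mL.
- Ratio = √(155/194) = 0.894, so the interval is 10.6% too narrow.
- Effective critical value = 1.96 × 0.894 = 1.752.
- One-sided type I error = 1 − Φ(1.752) = 4.0%; coverage of the two-sided interval = 92.0%.

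A simulation of 400,000 trials at a true difference of −400 ng/mL, with 155 normal observations per arm, gave 2.5% with n = 155 in the standard error and 4.0% with n = 194.

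**Step 3: dependence on the share excluded from PP2** (an assumption, taken equal in both arms). The ratio is √(1 − d), and the error is 1 − Φ(1.96 × ratio).

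| Excluded, d | Ratio | Coverage | One-sided error |
|---|---|---|---|
| 2% | 0.990 | 94.8% | 2.6% |
| 5% | 0.975 | 94.4% | 2.8% |
| 10% | 0.949 | 93.7% | 3.1% |
| 20% | 0.894 | 92.0% | 4.0% |
| 30% | 0.837 | 89.9% | 5.1% |

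**Step 4: the composite** (exact binomial enumeration at the margin, 65% against 52.5%).

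| Proportions from | n in the SE | One-sided error |
|---|---|---|
| 155 per arm | 155 | 2.5% |
| 194 per arm | 194 | 2.6% |
| 155 per arm | 194 | 4.2% |

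The second row is the formula as worded, and its standard error is sound. Only the mixed third row inflates the error. At the planned rates of 65% and 67.5% that mixture would give a half-width of 9.4 instead of 10.5 percentage points, but no section asks for it.

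**The case against.** The strongest reply is that this is loose notation. Section 11.12 bases the ferritin power on evaluable patients, and section 4 keeps randomised and evaluable numbers apart. Standard software would also take n from the PP2 data, so the inflation needs someone to insert the randomised count by hand. This is a fair account of what was probably intended. It does not make the stated formula right, since the definition is explicit and nothing elsewhere overrides it.

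The reply also points out that 4.0% belongs to 20% exclusion, while section 11.13 expects very little missing data. This stands: at 2% to 5% excluded the error is only 2.6% to 2.8%. The trial was nevertheless sized for 20% loss, so 4.0% is a scenario of the plan's own making.

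The ferritin test is secondary, meant to help interpret the composite, carries no multiplicity adjustment, and is backed by an ITT analysis. This also stands and limits the consequence. The ITT analysis does not clearly remove the fault, however. The failure rule concerns the binary composite, and section 11.13 confines imputation to missed visits in the trend analysis. No rule supplies a missing month-12 value for the ferritin mean.

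A reader might infer two stronger things that the documents do not support:

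- **That the primary type I error exceeds 2.5%.** The composite formula takes p and n from the same patients, and its wording directly follows the ITT failure rule. What is shown is a mismatch with PP1, not an interval that is too narrow.
- **That the −400 ng/mL rule may point the wrong way.** The mean change is described as lying between baseline and end of treatment. Read in that order it is baseline minus end, which fits a lower limit above −400. No error is shown.

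**Conclusion.** The point holds for ferritin as a conditional error. If the definition of n is applied as written to PP2 estimates, the interval is 10.6% too narrow and the one-sided error is 4.0% at the planned 20% loss, falling to about 2.6% at 2% loss. These figures assume a common SD of 1000 ng/mL, equal exclusion in both arms, and exclusion that does not itself bias the PP2 comparison.

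For the composite, the verdict is limited to definitions: n and p are set on randomised patients, while PP1 is primary and ITT requires started therapy. Inflation to 4.2% would arise only from combining PP1 proportions with randomised counts.

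The correction should be made because both formulas are prespecified for non-inferiority claims. It does not call the sample size or the confirmatory error rate into question.

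**What to change.** In section 11.6, add one sentence to each formula:

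- **Composite:** p_1, p_2, n_1 and n_2 are computed on the patients of each arm in the analysis set being used (PP1 for the primary analysis, ITT for the corroborating one).
- **Ferritin:** m_1, m_2, the pooled variance, n_1 and n_2 are computed on the patients of each arm in the analysis set being used (PP2, or ITT for corroboration).

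Optionally, and only as a clarification, state that m is baseline minus month 12.

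The cost is two sentences. The margins, sample size and data collection stay as they are, and the power statements in section 11.12 already rest on evaluable patients.
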